## **6.6. Ethical Principles**

This study will be conducted in accordance with the principles of the current Declaration of Helsinki (Ethical Principles for Medical Research Involving Human Subjects) and with the NHMRC National Statement on Ethical Conduct in Human Research 2007 (updated 2018). The conduct of the study will be in accordance with the ICH Integrated Addendum to E6(R1): Guideline for GCP ICH E6(R2), annotated with any applicable country specific amendments.

This study will be conducted under a protocol reviewed and approved by an IEC and investigations will be undertaken by scientifically and medically qualified persons, where the benefits of the study are in proportion to the risks.

## 7. TRIAL OBJECTIVES AND PURPOSE

### 7.1. Objectives

#### 7.1.1. Primary Objectives

The primary objective of the study is to evaluate the ocular safety and tolerability of EXN407 ophthalmic solution in subjects with diabetic macular edema (DME) secondary to diabetes mellitus.

#### 7.1.2. Secondary Objectives

The secondary objectives of the study are:

- *Safety*: To evaluate the systemic safety and tolerability of EXN407 ophthalmic solution in subjects with DME secondary to diabetes mellitus
- *Safety*: To evaluate changes in ocular functional and structural measures with the use of EXN407 ophthalmic solution in subjects with DME secondary to diabetes mellitus
- *Pharmacokinetics*: To evaluate the systemic pharmacokinetics of EXN407 ophthalmic solution in subjects with DME secondary to diabetes mellitus

#### 7.1.3. [REDACTED]

[REDACTED]

[REDACTED]

[REDACTED]

[REDACTED]

[REDACTED]

## 7.2. Endpoints

### 7.2.1. Safety and Tolerability

The safety and tolerability endpoints of the study are:

- Primary:
  - Frequency and severity of ocular AEs in the study and contralateral eyes
- Secondary:
  - Frequency and severity of non-ocular AEs
  - Changes from baseline in safety parameters, including vital sign measurements, physical examination findings, ECG, and laboratory parameters
  - Changes from baseline in ophthalmic examination findings, including ophthalmoscopy.

### 7.2.2. Safety

Secondary endpoints that relate to safety are:

- Changes from baseline in Center-Subfield Macula Edema (center-subfield measure)
- Changes from baseline in macular fluid volume
- Change from baseline in BCVA using the ETDRS visual acuity scale
- Change from baseline in FFA
- Change from baseline in corneal thickness based on pachymetry assessed at a consistent time of day
- Change from baseline in corneal endothelial cell count (dose expansion cohort)

### 7.2.3. Pharmacokinetics

The PK endpoints of the study are:

Characterize the PK profile of EXN407 in plasma (dose escalation and dose expansion cohort[s]).

### 7.2.4. [REDACTED]

[REDACTED]

## 8. INVESTIGATIONAL PLAN

### 8.1. Overall Study Design

This FIH, Phase Ib/II study of EXN407 is a randomized, double-masked, vehicle-controlled multiple dose, dose-escalating study to evaluate the safety and tolerability of EXN407 in subjects with center involved DME, with CMT between 280-420  $\mu\text{m}$  and BCVA better than or equal to a 69 ETDRS score (an approximate Snellen equivalent of 20/40 or 6/12) in the study eye, which is considered secondary to diabetes mellitus. For brevity, the BCVA criteria will be noted as "better than or equal to 69 ETDRS score".

A schematic of the study design is provided in [Figure 1](#).

Study visits and assessments will occur as delineated in the Schedule of Assessments presented in [Table 5](#).

The Screening period is from 28 to 3 days prior to randomization and the start of study treatment (i.e., from study days -28 to -3). Subjects that meet all eligibility criteria at Screening will enter a run-in period (from post-screening to Day -1) where the subject (or subject's partner as applicable) will administer eye drops BID using Systane Ultra UD droppers. The run-in period serves to familiarize and train subjects in topical administration via eye dropper. Please refer to [Section 12.2](#) for more details on the run-in period. The task of instructing subjects in self-administration of study treatment will be performed by appropriately qualified, trained and delegated site staff.

Re-screening could take place for back up subjects (who qualified for the study, but were not randomized immediately due to places in the current cohort filling up) or for subjects who did not meet all Inclusion Criteria or who meet an exclusion criterion initially, but due to a change in clinical condition may have become eligible. Please refer to [Section 8.3.1.1](#) for more details on re-screening procedure and criteria.

#### *Selection of Study Eye*

EXN407 or vehicle-control solution will be administered unilaterally to the study eye only. The Investigator should identify the eye in which evident center involved DME is present with a CMT between 280-420  $\mu\text{m}$  as determined by SD-OCT and meeting all other inclusion/exclusion criteria. All SD-OCT assessments for a subject should be taken with the same make and model of equipment throughout the duration of the study.

If both eyes qualify on the basis of evident DME with CMT of between 280-420  $\mu\text{m}$ , and other inclusion/exclusion criteria, then the Investigator should choose the eye with the worse (greater) CMT as the study eye. If CMT is the same, then the eye with worse visual function as assessed by BCVA will be selected as the study eye. If both eyes have the same BCVA then the right eye will be selected.

#### *Dose Escalation (A) Cohorts*

The study will assess the safety and tolerability of EXN407 at up to three escalating dose (concentration) levels and placebo (vehicle) consisting of an excipient formulation adjusted for osmolality. EXN407 or vehicle-control will be administered as a single 30  $\mu\text{L}$  drop by unilateral eye drop administration to the study eye only, and the drops will be dosed BID for 7 days.

Subjects will be assessed throughout the treatment period for safety, tolerability and efficacy at follow-up visits.

#### *Analysis and Adaptive Design*

All visit-based data will be analyzed for the study eye at each visit and assessed for any change from baseline. Comparisons with the non-dosed contralateral eye will also be evaluated in each subject. All protocol evaluations will also be completed on the non-dosed contralateral eye. No vehicle-control or other study treatments will be administered to the contralateral eye. The response to active treatment will be compared to vehicle on a group basis (pooling vehicle subjects).

The protocol is adaptive regarding the number and size of cohorts and dose level progression, which will be informed by emergent data and recommendation by the DEC following review of available safety and tolerability data from each cohort. The number of dose levels proposed in this protocol can potentially be reduced or altered based on DEC review and Sponsor decision.

#### *Allocation to Study Treatment*

With exception of the first subject cohort, each of the remaining ascending dose subject cohorts will consist of four subjects (3 subjects randomized to receive EXN407 and 1 subject randomized to receive placebo). Of note, the first cohort will incorporate an additional subject to provide a sentinel dosing subgroup (2 subjects, 1 subject randomized to receive EXN407 and 1 subject randomized to receive placebo) followed after an interval of at least one week by the remaining subjects (2 subjects randomized to receive EXN407 and 1 subject randomized to receive placebo).

There is no sentinel dosing subgroup in any of the remaining ascending dose subject cohorts. The rationale for not implementing a sentinel dosing subgroup for subsequent cohorts is multifactorial, considering the lack of toxicity findings in preclinical studies, the route of administration (topical rather than systemic), the target not being novel or immunomodulatory, and the increment in escalating doses being small.

The interval between cohorts, and between the sentinel pair and the remainder of the first cohort, will be at least 7 days.

Each eligible subject in the dose escalation cohorts (numbered cohorts 1, 2, 3, etc.) will receive EXN407 or vehicle BID over a 7 day period (1 drop of 30 µL at each dosing occasion, therefore 14 drops in total; with the contingency that if the first drop is not properly administered a second drop can be administered at the time).

#### *Dose Expansion (E) Cohort*

The highest well-tolerated dose of EXN407 (as recommended by the DEC) will be evaluated in a subject expansion cohort consisting of up to a maximum of 40 subjects (randomized to receive EXN407 at the selected dose or vehicle). Each eligible subject in the expansion cohort will receive study drug for up to 84 days, resulting in a total of 168 doses (168 single drops of 30 µL volume) of EXN407 or vehicle.

Subjects who do not meet individual subject stopping criteria at the clinical evaluation visits will continue dosing until the final day of dosing. Subjects who meet the stopping criteria will be discontinued from dosing but continue to receive safety and efficacy evaluation and all

scheduled clinical assessments as well as follow-up at an EOS Visit 28 days post the subject's last dose.

Detailed stopping criteria and guidance for Investigators are provided in [Section 8.5](#).

## 8.2. Number of Subjects

Up to approximately 48 subjects will be enrolled into this study.

- Three (3) subjects are expected to be randomized to low-dose, 2 subjects are expected to be randomized to placebo (cohort 1, N=5 total)
- Three (3) subjects to mid-dose, 1 subject to placebo (expected to be cohort 2, N=4 total)
- Three (3) subjects to high-dose, 1 subject to placebo (expected to be cohort 3, N=4 total).

The remaining subjects (up to 40 additional subjects) will potentially be assigned to additional cohorts of four subjects at a given dose level (three EXN407 subjects, one placebo subject), and the remainder will be assigned to the dose expansion cohort once the highest well-tolerated dose is identified. Decisions to escalate to the next higher dose level, to recruit an additional cohort at the same dose level, or to move to the dose expansion cohort, are dependent on emergent data and the outcome of near real-time safety review by the DEC. An algorithm regarding progression to cohort expansion will be defined in the DEC charter.

The sample size for this study is deemed to be sufficient to evaluate the safety and tolerability of EXN407 in this population and to gather efficacy data that will aid in powering future clinical trials.

The final number of subjects is dependent on whether any dose levels are expanded following evaluation of emergent data by the DEC but is not expected to exceed approximately 48 enrolled subjects in total.

As the main aim of this study is to generate information on the safety and tolerability of EXN407, subjects who are withdrawn from the study for reasons other than safety issues may be replaced at the discretion of the Sponsor and the Investigator.

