***Dose Expansion (E) Cohort***

The highest well-tolerated dose of EXN407 (as recommended by the DEC) will be evaluated in a subject expansion cohort consisting of up to a maximum of 40 subjects (randomized to receive EXN407 at the selected dose or vehicle, in a 2:1 ratio). Each eligible subject in the expansion cohort will receive study drug for up to 84 days, resulting in a total of 168 doses (168 single drops 30  $\mu$ L volume) of EXN407 or vehicle.

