***Number of Subjects (Planned):***

Up to approximately 48 subjects are planned to be enrolled in the study:

- Three (3) subjects are expected to be randomized to low-dose, 2 subjects are expected to be randomized to placebo (cohort 1, N=5 total).
- Three (3) subjects to mid-dose, 1 subject to placebo (cohort 2, N=4 total).
- Three (3) subjects to high-dose, 1 subject to placebo (cohort 3, N=4 total).
- The remaining subjects (up to 40 additional subjects) will be assigned to maintain/down-dose cohorts and/or expand to additional cohorts at the same dose level, dependent on emergent data and the outcome of near real-time safety review by the DEC.

An algorithm regarding progression to cohort expansion will be defined in the DEC charter. The final number of subjects is dependent on whether any dose levels are repeated and which dose is expanded, following evaluation of emergent data by the DEC but is not expected to exceed approximately 48 enrolled subjects in total.

As the main aim of this study is to generate information on the safety and tolerability of EXN407, subjects who are withdrawn from the study for reasons other than safety issues may be replaced at the discretion of the Sponsor and the Investigator.

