##### *Cohorts 2 Onward*

Following DEC evaluation and approval of the safety of the previous dose level, the next higher dose level may initiate dosing for four subjects, who will be clinically evaluated at 48 hours, 72 hours and 7 days post-dose initiation (Day 8). Following completion of the 1-week clinical assessment comprising 7 days of continuous dosing, the DEC will review the safety and tolerability data. Once all applicable data at the 1-week point are reviewed and judged

satisfactory by the DEC, a recommendation to the Sponsor will be made and documented regarding dose progression.

Alternatively, safety data from the previous cohort may result in a DEC recommendation to repeat the previous dose level in the next sequential numbered cohort for an additional four subjects. These additional subjects will be clinically evaluated at 48 hours, 72 hours and 7 days post-dose initiation (Day 8). If the DEC judge the additional safety and tolerability data at that dose level to be satisfactory, a recommendation will be made and documented regarding dose progression and the next higher dose level can initiate dosing in the next sequential numbered cohort.

As there are three dose levels (low-, mid- and high-dose) with this adaptive design there can be as many as six dose escalation cohorts following the sentinel pair (should there be two cohorts at each dose level due to safety and tolerability findings at each DEC meeting).

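### On the planned three-cohort path the sample-size components sum to 53 (5 + 4 + 4 + up to 40), 5 more than the stated total of approximately 48

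*Combined protocol and SAP*

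**What the plan says.** The planned sample size is set out in two places, the synopsis (Number of Subjects) and Section 8.2, and both carry the same figures.

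- **Total.** The synopsis says "Up to approximately 48 subjects are planned to be enrolled in the study". Section 8.2 gives the same number, and both add that the final count depends on dose escalation committee (DEC) decisions "but is not expected to exceed approximately 48 enrolled subjects in total".
- **Escalation cohorts.** Both list cohort 1 with 5 subjects (3 low-dose, 2 placebo), cohort 2 with 4 (3 mid-dose, 1 placebo) and cohort 3 with 4 (3 high-dose, 1 placebo).
- **Further subjects.** Section 8.2 continues: "The remaining subjects (up to 40 additional subjects) will potentially be assigned to additional cohorts of four subjects" at a given dose level, "and the remainder will be assigned to the dose expansion cohort once the highest well-tolerated dose is identified". The synopsis has a looser version: "The remaining subjects (up to 40 additional subjects) will be assigned to maintain/down-dose cohorts" and/or to further cohorts at the same dose level.

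Three other places bear on the count. The synopsis, Section 6.4.3 and Section 8.1 each describe a "subject expansion cohort consisting of up to a maximum of 40 subjects". Section 6.4.2 allows for repeated dose levels, so that "there can be as many as six dose escalation cohorts following the sentinel pair". Section 8.1 (Analysis and Adaptive Design) lets the number of dose levels be reduced or altered after DEC review.

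**The concern.** The 40 cannot include the 13. It follows them in the list, and it is described as both remaining and additional. If remaining means what is left of 48 after three cohorts, the figure should be 35. If 40 is right, the total should be 53. The two passages that define the enrolment ceiling of this first-in-human study therefore give a total that does not equal its parts on the path the protocol expects. A site or ethics committee reading them cannot tell whether the upper limit on further subjects after three escalation cohorts is about 35 or 40, or whether the approved ceiling is 48 or 53.

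**Working it through.** There is no power calculation to reproduce. Section 18 states that there is no formal hypothesis testing, so the sample size is a count of subjects by cohort. The check is whether the stated total equals the sum of its stated parts.

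**Inputs (synopsis and Section 8.2):** cohort 1 = 5; cohort 2 = 4; cohort 3 = 4; further subjects = up to 40; stated total = approximately 48.

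**Planned path**

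- Escalation: 5 + 4 + 4 = 13
- Sum of parts: 13 + 40 = 53
- Excess over the stated total: 53 − 48 = 5, and 5/48 = 10.4%
- Places left under 48: 48 − 13 = 35

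The stated figure of 48 is not reproduced.

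**Does it depend on where escalation stops?** The design allows fewer dose levels, so each stopping point was checked.

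| Escalation ends after | Escalation subjects | Plus 40 | Difference from 48 | Places left under 48, capped at 40 |
|---|---|---|---|---|
| Cohort 1 | 5 | 45 | −3 | min(40, 43) = 40 |
| Cohort 2 | 9 | 49 | +1 (2.1%) | 39 |
| Cohort 3 (planned) | 13 | 53 | +5 (10.4%) | 35 |

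The first two rows are compatible with a ceiling of about 48. The third is not. A total of exactly 48 with 40 further subjects would need 48 − 40 = 8 escalation subjects, and the planned cohorts give 5, 9 or 13.

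**Is three cohorts the expected path?** Section 8.2 labels the mid- and high-dose groups as the expected cohorts 2 and 3, and Section 6.4 plans three or more sequential cohorts. It is.

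**Repeat cohorts.** Section 8.2 takes repeat cohorts of four out of the 40, so they do not raise the sum above 53. They do reduce expansion. With all three dose levels and 0, 1, 2 or 3 repeats, escalation takes 13, 17, 21 or 25 subjects. The last is the six-cohort maximum: 5 + 5 × 4 = 25. Expansion is then limited to:

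- 35, 31, 27 or 23 if 48 governs (48 minus escalation)
- 40, 36, 32 or 28 if 53 governs (53 minus escalation)

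The two readings differ by 5 places throughout.

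**The case against.** The strongest reply is that every number here is soft. The total is approximate and is only an expectation, the 40 is an upper limit, and cohorts 2 and 3 are described as expected. In an adaptive design the component maxima need not all be reached together. The plan can be carried out within 48 as written, by enrolling 13 in escalation and no more than 35 afterwards.

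Most of this stands. It means that the conflict is between ceilings and that the plan is workable. It does not remove the mismatch, because 48 is itself given as the upper limit and nothing says which limit gives way. A gap of 5 in 48, on the expected path, is more than approximately can reasonably cover; the gap of 1 after two cohorts is not.

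Several stronger readings are tempting, and the documents do not support them.

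- **That the expansion maximum of 40 in the synopsis, 6.4.3 and 8.1 contradicts 8.2.** A cohort of "up to a maximum of 40 subjects (randomized to receive EXN407 at the selected dose or vehicle") stays true as an upper limit whether the total is 48 or 53.
- **That enrolment could reach 25 + 40 = 65.** This treats the expansion maximum as separate from repeat cohorts, but Section 8.2 draws repeats from the same 40.
- **That the sharing of the 40 between repeats and expansion appears only in 8.2.** The synopsis also assigns the 40 to maintained, reduced-dose or additional cohorts. Only the detail (cohorts of four, with the remainder to expansion) is specific to 8.2.
- **That a smaller expansion undermines the safety precision.** The plan sets no precision target, so there is nothing to miss.

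**Conclusion.** The point holds as a consistency error in the synopsis and Section 8.2. On the planned three-cohort path the stated parts sum to 53 against a stated total of approximately 48, an excess of 5 subjects (10.4%). Equivalently, a total of 48 leaves about 35 further places where the text allows up to 40. The conclusion rests on reading the 40 as additional to the 13, as both passages say, and on all three planned cohorts being filled. It does not hold if escalation stops after cohort 1 or 2.

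A reader might infer that the sample size is inadequate or that an analysis is invalidated. Neither follows: Section 8.2 claims only that the number is sufficient to evaluate safety and tolerability and to gather data for powering later trials, and Section 18 keeps the analysis descriptive. Nor do the documents show which of 48 and 40 is the wrong figure.

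**What to change.** In the synopsis (Number of Subjects) and Section 8.2, the sponsor should state which figure governs and make the total equal its parts. There are two consistent options.

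- **(a) Keep approximately 48.** Limit the further subjects (repeat cohorts plus expansion) to the places remaining under 48: about 35 after three cohorts, and never more than 40. This adds no patients. The cost is a smaller stated expansion on the planned path. With no repeat cohorts, the 2:1 randomization gives about 23:12 from 35, against about 27:13 from 40. Up to 40 places remain available if escalation stops after cohort 1, and 39 if it stops after cohort 2.
- **(b) Keep up to 40 further subjects.** Restate the total as up to approximately 53, with repeat cohorts still taken from the 40. This raises the enrolment ceiling by 5 (10.4%).

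Under either option the sponsor should say whether replacements count toward the total. The synopsis and Sections 8.2 and 15.2 provide for replacing subjects, but no passage says whether the replacements fall inside or outside the ceiling. The new wording should not assume an answer, because excluding them could raise permitted enrolment above the current limit.

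The descriptions of the expansion cohort in the synopsis, 6.4.3 and 8.1 need no correction; a cross-reference to 8.2 there is optional. Either option is a text change that needs a protocol amendment, signed and submitted to the ethics committee as Section 25.1 requires.

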## 8.3. Treatment Assignment

### 8.3.1. Randomization

██████████ Limited will prepare a system for randomization of subjects and will manage the randomization of eligible study subjects per this system. A randomization list will be prepared using a statistical software package by a ████████ Biostatistician.

Each subject will be provided with a unique screening number post-documentation of informed consent. Once deemed eligible for enrolment in the study, the subject will be assigned a sequential randomization number prior to first dosing. Subjects who withdraw from the study, for any reason, without completing all necessary Screening assessments will be considered screen failures. Re-screening of screen failures (subjects screen failed for any reason) can be

performed only with the agreement of the study MM (████████) / Sponsor MM. Please refer to [Section 8.3.1.1](#) for more details on the re-screening process.

### 8.3.1.1. Re-Screening

Re-screening will be allowed in this study. The two most likely scenarios in which re-screening will take place are listed below. Other scenarios will be considered on a case-by-case basis and at the Investigator's discretion and following MM approval. Out of range laboratory assessments from first screening are to be repeated at re-screening. If the subject is proficient in dropper use after their initial run-in, then a further run-in is not required.

- 1) Back up subjects during dose escalation, who qualified for the study but were not randomized due to the current cohort filling up, can be put forward for inclusion in the subsequent cohort. Dose escalation or dose expansion subjects who qualified for the study but were not randomized due to scheduling or other constraints may also be re-screened. If the screening window has elapsed, and subjects are able to complete Visit 1A or 1E within 8 weeks of initial Screening, the following assessments do not need to be repeated during re-screening:
  - Demographics: Screening assessments missed from first Screening should be performed, if possible
  - Medical, Surgical and Ocular History: only changes to previous recordings should be noted
  - Twelve-Lead ECG
  - Hematology
  - Serum Chemistry
  - Coagulation
  - Urinalysis
  - Follicle-stimulating hormone
  - Corneal Endothelial Cell Count (if conducted not more than 6 months before Visit 1A or 1E)
  - Fluorescein fundus angiography

The remaining Screening assessments that would still be done:

- Informed Consent
- Height and Weight
- Review of Eligibility Criteria
- SD-OCT
- Concomitant Medications

- Ophthalmic Exam
- BCVA
- Physical Exam
- Vital Sign Measurements
- Urine Pregnancy Test
- CFP
- IOP
- Corneal Pachymetry
- Out of range laboratory values

2) Subjects who did not meet all Inclusion Criteria or who meet an exclusion criterion initially, but due to a change in clinical condition may have become eligible, can be re-screened at the discretion of the Investigator (e.g., HbA1c >12% originally, but patient has reduced this through better disease management). In this scenario, with the concurrence of the Sponsor's MM, it will not be necessary to completely re-screen the subject, and the following assessments can be skipped (if previous readings were taken within the allocated timeframe):

- Corneal Endothelial Cell Count (if conducted not more than 6 months before Visit 1A or 1E)
- Fluorescein fundus angiography (if conducted not more than 8 weeks before Visit 1A or 1E)

